9.7.9.2. Self-control case-series

Background

The self-control case-series method (SCCS) was developed to investigate associations between vaccination and acute potential adverse events [Farrington, 1996]. The SCCS is based only on cases, and provides consistent estimates of the relative incidence. It controls implicitly for all fixed confounders, that is to say, confounders that do not vary with time over the observation period, e.g. genetics, location, socio-economic status, gender, individual frailty, severity of underlying disease.

The effect estimate is calculated as the ratio of the rate (or hazard) of events in a given post-exposure period (risk period), to the rate of events in the absence of the exposure (control period).

Risk and control periods

[figure not shown]
For the two co-primary endpoint analysis, the period at risk will be 12 months after the first dose of Cervarix. The control period will also be a period of 12 months after the risk period but separated by a buffer period of 6 months. The new events occurring during the buffer period will not be included in the model (Figure 5). A buffer period is defined to control the risk of late effect of vaccine (risk period for many auto-immune diseases is not clearly defined). We have judged reasonably that the vaccine effect if any will be absent after 18 months.

A sensitivity analysis of the co-primary endpoints will be carried out taking into account individual risk and control periods. For each subject the risk period is the period from the first dose of Cervarix until 6 months after the last dose, and the control period is the period from 6 months after the end of the risk period until month 30. This sensitivity analysis is an SCCS adjusted for the individual variability in the vaccination schedule.

For individual diseases (secondary endpoint), specific risk periods will be defined (Figure 5). SCCS analysis of individual diseases will be carried out only if there are at least 10 cases in the risk and the control periods.

Censoring will not be applied for this analysis, since date of death from the population register will not be available at the time.

Statistical Calculations

The statistical calculation will be done using the specific SAS macro developed by Whitaker et al. [Whitaker, 2006] and available online from http://statistics.open.ac.uk/sccs

Mathematical model

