For the SCCS analysis, the exposed female cohort will be followed during a total period of 30 months from the first dose. The risk period will be defined as one year after the first dose, including the six months after the last dose when the full three-dose vaccination course is administered. A control period of the same duration will be defined, excluding the periods after subsequent doses. To control for a possible late effect of the vaccine, the control and the risks period will be separated by a six-month buffer period (Figure 2). For analysis of individual diseases, specific risk period could be defined.

light 2 Och control case series analysis	Figure 2	Self-control	case-series	analysis
--	----------	--------------	-------------	----------

Note: all three doses may not have been administered

The SCCS uses each subject as its own control, preventing virtually all potential confounding factors which do not vary with time (e.g. socio-economic status, gender, location) [Whitaker, 2006]. Additionally, fewer cases are usually required, as compared to a case-control design. The control period is chosen subsequent to the at-risk period. Age bias is not anticipated because the follow-up period is short compared to the age effect on incidence of autoimmune diseases (see Table 1).

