9.3.3. Data to be collected

9.3.3.1. Subjects characteristics

The following data will be extracted for the analysis population:

• Demographic characteristics: birth month and birth year, sex, region, practice region identifier, date of death (if applicable) and acceptable patient flag

- CPRD GOLD information: CPRD GOLD start date, first registration date, current registration date, registration gaps, registration status, transfer-out date, transfer-out reason
- HES information: Linkage to HES data
- Vaccines:

Administration of any other vaccine from one year before the reference date and until the end of follow-up will be collected: date of vaccination, medcodes and immunization type will be extracted from the immunisation file. Cross-tabulation of medcodes and vaccine names/class is detailed in Annex 5.

• Health care resource utilization: number of primary care resource utilization during the year before the reference date.

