9.5. Study size

9.5.1. Sample size for cohort design

The target sample size is 50,000 subjects in each cohort. The relative risk (RR) that would be detected with 80% power and alpha = 0.05 is given in Figure 3 versus the incidence rate in the (Cervarix) unexposed cohort. The detectable difference in incidence rate (= additional cases per 100,000 person-years) is also depicted.

(Method: Comparison of two independent proportions using a likelihood ratio test, PASS 2005)

Cohorts of 50,000 subjects each should allow detection, with 80% power, of a RR between 3.7 and 18.7 for the neuro-inflammatory NOAD (incidence rate between 10 and 1/100,000 person-years) and between 1.6 and 2.0 for other NOAD (incidence rate between 100 and 50/100,000 person-years).

Because of risk of lost to follow-up, the sample size is increased by approximately 30% in each cohort to approx. 65,000 subjects.

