9.7.5. Analysis of co-primary endpoints

9.7.5.1. Cohort analysis

The primary analysis will compare the incidence rates of the primary outcomes of interest between the Cervarix exposed female cohort and the historical unexposed female cohort. Results will be presented as the incidence rate ratio and the incidence difference. Exposed person-time will be defined as the period between the reference date and the earliest of the following events:

- End of study period (defined as 12 months after the reference date);
- Date of de-enrolment from CPRD GOLD;
- Date of unspecified HPV vaccine or Gardasil or Cervarix for unexposed cohort;
- Date of first diagnosis of the outcome of interest.

Incidence rates for auto-immune diseases will be calculated by dividing the number of cases by person-time. A Poisson regression model will estimate the risk ratio and its 95% confidence interval. The Poisson model will include the number of cases in each cohort as the dependent variable, the exposure status as a binary independent variable, the age-group ([9-18],[18-25]) as a covariate, and the log-transformed total person-year as an offset.

Sensitivity analyses

Sensitivity analyses will be performed:

- Incidence rates for NOAD in the exposed cohort will be calculated after each dose by dividing the number of cases by the total person-time. Exposed person-time will be defined as the period between the date of the dose administration and the earliest of the following events:
 - End of risk period (defined as 6 months after each dose);
 - Date of the next Cervarix dose;
 - Date of de-enrolment from CPRD GOLD;

- Date of unspecified HPV vaccine or Gardasil;
- Date of first diagnosis of the outcome of interest.
- Separate analysis will be performed for subjects younger/older than 18 years.
- Analysis including possible confounding factors (if available): other vaccination, age, region, healthcare resource utilization, categorization will be determined based on the available data.
- In case of more than 5% of NOAD with unknown/incomplete date, a sensitivity analysis will be done including these events as occurring during the risk period. This imputation will be done for the four cohorts.
- The same comparison will be done between the two male cohorts. In case of significant difference between these two male cohorts, the primary analysis will be adjusted for time effect other than Cervarix (see Section 9.7.5.1 for the detailed statistical models).

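### The SCCS rules out censoring although its control window always comes last, so girls leaving CPRD would by themselves push the rate ratio above 1; the rule also conflicts with the model in the same section

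*Protocol*

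**What the plan says.** Protocol section 9.7.9.2 sets the SCCS windows for both co-primary composites: "the period at risk will be 12 months after the first dose of Cervarix", and "The control period will also be a period of 12 months after the risk period but separated by a buffer period of 6 months". Section 9.1.2 gives the span: "For the SCCS analysis, the exposed female cohort will be followed during a total period of 30 months from the first dose". The sensitivity analysis with individual vaccination schedules also runs its control period to month 30. On follow-up, section 9.7.9.2 then says: "Censoring will not be applied for this analysis, since date of death from the population register will not be available at the time".

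Other places point the other way:
- The mathematical model in section 9.7.9.2 gives each individual her own observation interval [a_i, b_i] and defines e_ik as the time she spends in period k.
- Section 9.3.3.1 extracts "registration status, transfer-out date, transfer-out reason" and "practice region identifier, date of death (if applicable) and acceptable patient flag".
- Section 9.7.5.1 ends cohort person-time at, among other events, "Date of de-enrolment from CPRD GOLD".
- Section 9.5.1 expects losses: "Because of risk of lost to follow-up, the sample size is increased by approximately 30% in each cohort to approx. 65,000 subjects".

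No section requires registration to month 30. The inclusion criteria (9.2.4.1) look back 12 months only. The disposition list (9.7.3) refers to registration during the study period, which section 9.7.5.1 puts at 12 months after the reference date.

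**The concern.** A case enters the SCCS only if it is recorded (section 9.7.2.2), and it can be recorded only while the girl is registered. Since the control window is always the later one, leaving removes more control-period cases than risk-period cases. Without censoring, the time lost is not removed from the control period, so its rate is understated and the ratio rises with no vaccine effect.

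The stated reason does not support the rule. A missing register date of death says nothing about transfer to another practice, and section 9.3.3.1 lists both a transfer-out date and a date of death.

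Section 9.7.1.2 tests both co-primary composites in the SCCS without alpha adjustment. The SCCS is also the analysis that does not depend on the historical comparator. Ordinary practice transfers could therefore be read as a vaccine signal, and the sensitivity analysis, which has the same month-30 end, would not show the problem.

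**Working it through.** **The plan's own figure.** Table 4 gives 194, 68, 29 and 15 cases for rate ratios 1.5, 2, 3 and 5. The signed-root likelihood-ratio formula is n = (z_a + z_b√B)²/A, with r = 0.5, q = IRR·r/(IRR·r + 1 − r), A = 2[q·ln IRR − ln(IRR·r + 1 − r)] and B = (ln IRR)²·q(1 − q)/A. At two-sided 0.05 and 80% power it gives 193.7, 68.1, 28.8 and 14.9. Table 4 is reproduced up to rounding, which confirms the equal 12:12-month design.

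**Bias from loss alone.** With equal windows and no censoring, the estimate is the number of risk-period cases divided by the number of control-period cases. Assume a true ratio of 1, constant incidence and a constant leaving hazard h per year.
- Observed risk time per girl: (1 − e^(−h))/h
- Observed control time per girl: (e^(−1.5h) − e^(−2.5h))/h
- Expected ratio: e^(1.5h)

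The leaving rates below are assumptions, because the protocol gives none for 30 months.

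| Assumed loss | h | Risk time (y) | Control time (y) | Null ratio |
|---|---|---|---|---|
| 5% a year | 0.0513 | 0.975 | 0.903 | 1.08 |
| 10% a year | 0.1054 | 0.949 | 0.810 | 1.17 |
| 23% lost by month 30 | 0.1049 | 0.949 | 0.811 | 1.17 |
| Median follow-up 5.0 y (section 9.4.1) | 0.1386 | 0.934 | 0.758 | 1.23 |
| 23% lost every year | 0.2624 | 0.880 | 0.593 | 1.48 |

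The 23% is 1 − 50,000/65,000, from section 9.5.1. If every girl is registered to month 12 and leaves only afterwards, risk time is 1 and the ratio falls to 1.11 (10% a year) or 1.15 (median 5.0 years).

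The disease-specific windows in section 9.7.6 (2 and 22 months, 6 and 18 months) also have midpoints 1.5 years apart. At 10% a year both give 1.17.

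**False-positive rate at 10% a year.** Take 65,000 girls, the incidences in section 9.5.1, and a Wald test on the log ratio: ln(1.1712) = 0.158, SE = √(1/n_risk + 1/n_control).

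| Incidence per 100,000 | Expected cases, risk / control | SE | z | Two-sided rejection |
|---|---|---|---|---|
| 100 (other) | 61.7 / 52.7 | 0.188 | 0.84 | 13% |
| 50 (other) | 30.8 / 26.3 | 0.265 | 0.60 | 9% |
| 10 (neuroinflammatory) | 6.2 / 5.3 | 0.593 | 0.27 | 6% |
| 1 (neuroinflammatory) | 0.6 / 0.5 | 1.876 | 0.08 | 5% |

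The last two rows are rough, because the counts are too small for the Wald approximation.

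**Check of the repair.** Simulating the conditional likelihood with no vaccine effect, and with e_ik cut at the leaving date, returned 1.00 at hazards for 5% a year, 10% a year, median 5.0 years and 23% a year. The same simulations without censoring gave 1.08, 1.17, 1.23 and 1.48.

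**The case against.** **The full 30 months is an inference.** No sentence credits every case with 30 months. The model's e_ik, taken literally, gives an early leaver less control time, and the no-censoring sentence can be read as concerning death only. This stands in part: the protocol contradicts itself, and the bias follows only if the no-censoring rule governs. The rule is worded without limit, however, and an analyst could follow it.

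**The size could be read too high.** A reader might take the 30% inflation in section 9.5.1 as 23% loss in every year and conclude that the null ratio is 1.48. The documents do not support that. The figure is a planning margin for the cohort sample size and has no stated horizon; reached by month 30, it gives 1.17. The 1.48 is an extreme scenario.

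**A serious false-positive rate for both composites might be inferred.** At the protocol's 1-10 per 100,000, the neuroinflammatory test is barely affected, although its estimate carries the same bias.

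**The net direction is not established.** The model has no age term. Table 1 shows UK female incidence rising with age for multiple sclerosis (0.9 at 15-19, 5.9 at 20-24) and lupus (2.3 at 10-19, 4.7 at 20-29), which pushes the ratio down. For type 1 diabetes it is lower in the older band (26.0 at 10-19, 10.1 at 15-34), which would push it up. So only the loss component is known to be upward. A second uncontrolled bias does not make the first acceptable.

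**The primary result might be thought at risk.** It is not. Section 9.7.5.1 makes the female cohort comparison primary and stops person-time at de-enrolment, and section 9.7.6 calls the individual-disease analyses non-confirmatory.

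**Conclusion.** The point holds for the SCCS and should be fixed. The no-censoring rule conflicts with the model's individual observation time, with the extracted leaving dates and with the cohort analysis, and its stated reason does not cover transfer-out. If it is followed, loss alone moves the null ratio to roughly 1.1-1.25 under the more plausible assumed leaving rates, at the lower end of that range if registration for the first 12 months is enforced. These sizes rest on constant incidence and a constant leaving hazard. The ratio the planned SCCS would finally report could be higher or lower, because age is also unmodelled.

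**What to change.** Replace the no-censoring sentence in section 9.7.9.2 with:

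> Each case's observation ends at the earliest of transfer-out date, date of death recorded in CPRD, practice last-collection date and month 30, and e_ik is computed from observed time in each period.

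Apply it to the co-primary, sensitivity and individual-disease SCCS. Cases who leave before month 18 then carry no control time in the co-primary analysis.

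Add the practice last-collection date to the extract in section 9.3.3.1. Transfer-out and death dates are listed there already; this one is not.

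The cost is one sentence, one added variable and slightly wider intervals. The cohort analysis needs no change.

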9.7.9.3. Scan Statistics

Scan statistics will be used to detect temporal clusters of cases. This is done by gradually scanning a window across time noting the number of observed and expected observations inside the window. The scanning window will be an interval of time. Two time window sizes will be used: 2 months and 4 months. The window with the maximum likelihood is the most likely cluster, that is, the cluster least likely to be due to chance. A p-value is assigned to this cluster. Since two time windows will be used, p-values will be compared to a Bonferroni adjusted alpha ($\alpha/2 = 0.025$). Scan statistics use a different probability model depending on the nature of the data. Under the null hypothesis, the observed events occur randomly following a uniform distribution according to a discrete Poisson model during the total observation period.

This scan statistics analysis will be done in each of the four cohorts to detect possible clustering of the two co-primary composite endpoints and of the individual diseases.

9.7.10. Conduct of analyses

9.7.10.1. Sequence of analyses

The study feasibility assessment is intended to confirm that the data are of sufficient quality to confirm the diagnoses, and that the target sample sizes can be reached. A brief report of the study feasibility assessment will tabulate the numbers of confirmed diagnoses and the number of vaccinees in the periods considered for the exposed and historical cohort.

The final analyses will be performed according to a two-step schedule:

- 1. Between-cohort analysis will be done when the primary and secondary endpoints occurring during the one-year follow-up period will be available for all subjects and the corresponding database will be frozen.
- 2. The SCCS analysis will be carried out when the primary and secondary endpoints occurring during the 30-month follow-up period will be available for all exposed female subjects and the corresponding database will be frozen.

9.7.10.2. Statistical considerations for interim analyses

There is no interim analysis.

9.7.10.3. Changes from planned analyses

Not applicable.

9.8. Quality control

Validation of clinical outcomes is described in Section 9.3.3 and Section 9.4.2.

Clinical data management will be performed in accordance with applicable GSK standards and data cleaning procedures.

The final study dataset will be archived and stored on a secured, access limited, computer platform SAS Drug Development (SDD) according to GSK Biological Standard Procedures. Specific statistical programs will be written in SAS 9.2 (or higher) and validated according to the GSK standard procedures. The validation of the quality control (QC) of the statistical analysis will be documented. All statistical programs, output files and QC documentation will be saved as read-only files on SDD.

The final study protocol and possible amendments, the final statistical report and the QC document, and the final study report(s) will be archived on a Document management system based on the Documentum platform: Computer Aided Regulatory Submission (CARS).

9.9. Limitations of the research methods

Limitations and recommendations for the research methods

As mentioned previously, Cervarix vaccination administration was done in the UK in the schools and administration of Cervarix is not reported for all subjects in CPRD. The vaccination record in the CPRD GOLD may not be complete; if for a certain subject no vaccination code for Cervarix is registered, vaccination status is uncertain. Due to the potential for under-reporting of HPV vaccination, an unexposed historical cohort (before introduction of Cervarix in the UK) was chosen instead of an unexposed concurrent cohort.

116239 (EPI-HPV-040 VS UK) Protocol FDA - EMA PASS Final Version 1

Although, diagnosis and/or coding of auto-immune diseases could change over time. Moreover, a link with HES was recently implemented in CPRD GOLD since 2009. The HES data coverage period is actually longer than 2009: currently April 1997 to March 2012. As such, historical controls will have the potential to have linked data in the same way as the more recent exposed group. In order to assess the possible impact of changes in auto-immune diseases diagnosis/coding in CPRD GOLD and HES over time, two male cohorts will also be enrolled: a cohort concurrent to the exposed female cohort and a historical cohort selected at the same time period as the unexposed historical female cohort. However, it is recognized that incidence of auto-immune diseases might vary according to sex as well as according to the age group. These two cohorts will be useful to study potential change over time in CPRD GOLD due to recent access to HES data that might increase the number of auto-immune diseases coded in the database.

A multitude of medcodes are used by the GP to enter diagnosis of autoimmune disease in CPRD GOLD. There is no ICD-10 code mapping. As far as possible , an exhaustive list of medcodes has been defined for each disease and specific algorithms have been developed. In addition, associated "free text" will be reviewed. However, risk of false positive cases (lack of specificity) could not be totally excluded. Lack of specificity can bias the risk ratio estimate to the null hypothesis. There can also be a risk of false negative (lack of sensitivity) however for a rare event, a lack of sensitivity does not bias the risk ratio estimation. Determination of the time to onset of first symptoms is also a limitation. Time between diagnosis and first symptoms is largely variable and depends on the disease and this is why not only medcodes will be used, but also HES and the free text when available.

The definition of the risk period for autoimmune disease is challenging. Too short a risk period would underestimate the actual risk whereas too long a risk period would dilute the actual risk. A period of one year after the first dose of Cervarix will be used for the co-primary composite endpoints. Analysis of the incidence rate of individual diseases will be used for a specific-disease risk period.

These limitations were addressed during a feasibility assessment: with the planned number of subjects for each cohort (65,000), the expected number of autoimmune disease cases to be reviewed should be around 280 cases, which is achievable with the developed methodology for case reviews.

10. **PROTECTION OF HUMAN SUBJECTS**

10.1. Regulatory and ethical considerations, including the informed consent process

The study will be conducted in accordance with all applicable regulatory requirements.

The study will be conducted in accordance with the Guidelines for Good Pharmacoepidemiology Practices (GPP) [ISPE, 2007], all applicable subject privacy requirements and the guiding principles of the Declaration of Helsinki.

Conduct of the study includes, but is not limited to, the following: CPRD GOLD's internal Independent Scientific Advisory Committee (ISAC) favourable approval of study protocol and any subsequent amendments. This approval has been obtained on August 30, 2012 (ISAC reference 12_086R, see Annex 4).

No patient informed consent will be obtained. The patient information in the CPRD GOLD database is fully coded and GSK Biologicals personnel will not be able to make a link between the data and specific individuals.

The CPRD GOLD has an ethical approval from a Multi-centre Research Ethics Committee (MREC) for purely observational research (i.e. studies that do not include patient involvement [Clinical Practice Research Datalink (CPRD GOLD) Website, 2012]).

